9.6 Data Management

9.6.1 Data Collection

In this study, data will be collected through an eCRF. Once the subject has provided his/her informed consent, the eCRF will provide a numeric subject identifier to anonymise the data within the eCRF. Only investigating sites will be able to link to numeric identifier to the subject.

The sponsor and the Contract Research Organisation (CRO) will ensure that an appropriate eCRF is developed to capture the data as required by the protocol.

Each site is required to have a computer and internet connection available for site entry of clinical data. All entries on the eCRF will be made under the electronic signature of the person performing the action (username and password). Only sponsor authorised users will be given access to the eCRF as appropriate for their study responsibilities. All users must have successfully undergone software application training prior to entering data into the eCRF.

Data will be monitored by a monitoring CRO according to an agreed Monitoring Plan. Any queries generated during the data management process will be tracked by the contracted data management CRO.

PAGE 31 OF 58

Data consistency and accuracy will be ensured by running real-time checks at time of data entry in the eCRF. Any queries and items not adequately explained will require additional queries to be raised to the investigator by the Data Management group for clarification/correction. The investigator must ensure that queries are dealt with promptly. All corrections to the eCRF data will automatically be tracked and a reason for the change will always be required. In the eCRF, the audit trail function will allow the changes and clarifications made to be viewed.

The investigator must, at a minimum, provide an electronic signature to each eCRF to attest to the accuracy and completeness of all the data. This electronic signature consists of an individual and confidential username and password combination. It is declared to be the legally binding equivalent of the handwritten signature.

Data management will be conducted by a CRO, under the supervision of the sponsor's Global Medical Affairs Clinical Operations. All data management procedures will be completed in accordance with Ipsen and the contracted CROs standard operating procedures (SOPs).

9.6.2 Data Archiving and Retention

After the study has been completed and clinical study report (CSR) approved, data will be stored in the Ipsen data repository.

Study documents will be archived in accordance with applicable regulatory requirements for a minimum of 10 years following study completion.

9.7 Data Analysis

9.7.1 Analysis Population Definitions

The following populations will be used during the statistical analyses:

- **Included population:** all subjects who signed the informed consent form (ICF);
- Full Analysis Set (FAS): all included subjects who have taken at least one dose of cabozantinib;
- **Safety population:** all included subjects who have taken at least one dose of cabozantinib and have a follow-up of safety;
- **Primary Safety population:** all subjects from the Safety population who started cabozantinib at the prescribed recommended dose.

9.7.2 Statistical and Analytical Methods

9.7.2.1 Statistical Analyses

The statistical analyses will be performed by an external CRO, managed by the sponsor's Biometry Department.

A statistical analysis plan (SAP) describing the planned statistical analysis in detail with tables, figures and listings templates will be developed as a separate document.

Statistical evaluation will be performed using Statistical Analysis System (SAS)[®] (Version 9 or higher).

As this is a noninterventional study, no formal statistical testing will be performed and all the analyses will be primarily descriptive in nature. When appropriate and unless otherwise specified, 2-sided 95% CIs will be displayed and if p-values are presented, they will be for exploratory purposes only.

Descriptive statistics will include number of available data, number of missing data and the following:

PAGE 32 OF 58

- Mean, standard deviation (SD), minimum, median, maximum and 95% CIs for means when appropriate for continuous variables;
- Frequency count and percentages for categorical nominal variables;
- Both the above for categorical ordinal variables.

Missing data will not be replaced but they will be displayed in all relevant tables (see Section 9.7.2.5.1).

9.7.2.2 Demographic and Other Baseline Characteristics

All demographic and baseline characteristics including disease characteristics will be listed for the FAS.

Demographics and baseline characteristics will include, age, age group (<65 years, ≥65 years), gender, use of tobacco, occupational status and sick leave status, weight, height, country and blood pressure, duration since disease diagnosis, stage at first diagnosis, stage at initiation of cabozantinib, IMDC and MSKCC risk group categories, therapy line (second line therapy or third and later line therapy), regimen at initiation (60 mg/day, other regimens), baseline bone metastasis (yes, no), ECOG performance-status score, number of prior VEGF-targeted therapies (1, 2, 3, 4 and >4), previous systemic therapy and planned frequency of radiological assessments during cabozantinib treatment.

Descriptive summary statistics for demographic and baseline characteristics will be presented by therapy line (second line or third and later line) and in total for the Primary Safety population and the FAS population. In addition, summaries will also be provided for the Safety population if it differs from the FAS population by at least 10% in total.

9.7.2.3 Subject Disposition and Withdrawals

The number of subjects included and number and percentage of subjects included but not part of the FAS will be provided in total.

The numbers and percentages of subjects included in each of the FAS, Primary Safety, and Safety populations will be tabulated by country, centre, therapy line and in total. The reasons for subject exclusions from each of the populations will also be tabulated by therapy line and in total. In addition, the numbers of subjects who discontinued and completed the study treatment will be tabulated for the FAS by therapy line and in total. Primary reasons for discontinuation of study treatment will also be tabulated for FAS by therapy line and in total.

9.7.2.4 Safety Evaluation

All safety data will be included in the subject data listings using the Safety population. Analyses and summary tables will be presented by therapy line and in total based on the Safety population and also on the Primary Safety population.

All AEs will be coded according to the Medical Dictionary for Regulatory Activities (MedDRA) and will be classified by MedDRA preferred term (PT) and system organ class (SOC). Adverse event listings will be presented by subject, SOC and PT.

The incidence of all reported AEs, TEAEs, SAEs, and treatment-emergent serious and nonserious AEs will be tabulated separately. In addition, summary tables for TEAEs will be presented by maximum intensity and drug relationship. Treatment emergent AEs associated with dose modification (temporary interruption, reduction or discontinuation) of study medication and TEAEs leading to cabozantinib temporary dose interruption, reduction or discontinuation will also be summarised separately.

A TEAE is defined as any AE that occurs during the administration of cabozantinib if:

PAGE 33 OF 58

- It was not present prior to receiving the first dose of cabozantinib; or
- It was present prior to receiving the first dose of cabozantinib but the intensity increased during treatment with cabozantinib.

All TEAEs will be flagged in the AE listings.

Summary statistics (mean, median, SD and range, as appropriate) will be presented for ECOG performance status, vital signs (blood pressure), and weight at each assessment. Changes from baseline to each postbaseline assessment will be summarised similarly.

Counts and percentages of normal and abnormal ECG findings will be presented at each assessment. In addition, shift from baseline to postbaseline assessments in ECG findings will also be presented.

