9.2.4 Study Duration

In the METEOR study, the median duration of exposure in subjects receiving cabozantinib was 8.3 months (Inter-Quartile Range 4.2 to 14.6).

PAGE 25 OF 58

Subjects will be followed up to 30 days after discontinuation of cabozantinib with a maximum follow-up per subject of 12 months from treatment initiation, even if the subject continues to receive cabozantinib.

The end of the study will be the date of the last study visit for the last subject in the study.

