9.2.8 Study Discontinuation/Withdrawal

If the subject permanently discontinues cabozantinib before Month 12, he/she will be withdrawn from the study.

The investigator may withdraw the subject from the study at any time for safety reasons or at his/her discretion. A subject may withdraw consent to participate in the study at any time.

In case of permanent treatment discontinuation between Visit 2 and Visit 8, the next visit should be completed along with the Study discontinuation form, approximately 30 days after the last dose of cabozantinib (see Table 1 and Section 9.2.7).

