11 MANAGEMENT AND REPORTING OF ADVERSE EVENTS

All AEs observed during the study are to be recorded on the eCRF. All AEs, regardless of relationship to study drug or procedure, should be collected beginning from the time the subject signs the ICF until the end of the study (see Table 1).

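### The TEAE definition ends with cabozantinib administration although AEs are collected for up to 30 days after the last dose, so new post-dose events are missing from the treatment-emergent tables

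*Protocol*

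**What the plan says.** Section 9.7.2.4 of the protocol fixes the definition: "A TEAE is defined as any AE that occurs during the administration of cabozantinib if" one of two conditions is met. The first is that the event was not there before the first dose. The second reads "It was present prior to receiving the first dose of cabozantinib but the intensity increased during treatment with cabozantinib". Both are tied to the time on drug. No interval after the last dose is added, and the protocol gives no other definition of a TEAE.

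The follow-up and collection rules reach further:

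- Section 9.2.4: "Subjects will be followed up to 30 days after discontinuation of cabozantinib with a maximum follow-up per subject of 12 months from treatment initiation".
- Section 9.2.8, for Visits 2 to 8 when the drug is stopped for good: "the next visit should be completed along with the Study discontinuation form, approximately 30 days after the last dose of cabozantinib". Footnote i of Table 1 says the same.
- Section 11: all AEs, whatever their relationship to the drug, "should be collected beginning from the time the subject signs the ICF until the end of the study".

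On reporting, Section 9.7.2.4 states: "The incidence of all reported AEs, TEAEs, SAEs, and treatment-emergent serious and nonserious AEs will be tabulated separately". It then plans tables by maximum intensity and by drug relationship, for TEAEs only, and flags TEAEs in the listings. Section 8.2.2 makes the description of treatment-emergent serious and nonserious AEs a secondary objective.

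**The concern.** The protocol sets up a safety window after the last dose and collects every AE in it. It then uses a definition under which an event that starts in that window cannot be treatment-emergent, and gives no reason for the difference. A severe AE that starts a few days after the last dose and is judged probably related would be collected, yet no planned AE table would show it by intensity or by relationship.

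At stake is a stated secondary objective of a post-authorisation safety study. The direction of the error is clear: treatment-emergent counts come out too low. Nor is this a detail left for the SAP. The protocol itself fixes the rule, so an SAP that added a post-dose window would depart from it, and one that followed it would carry the gap forward.

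A smaller ambiguity sits in the same sentence. It does not say whether an AE that starts during a temporary interruption occurs during administration.

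**Working it through.** No figure in the protocol depends on the TEAE definition, so there is none to reproduce. The check is first textual, then a rough sizing.

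**Which events are affected, taking the rules literally**

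| Event | TEAE under 9.7.2.4? | Where it is tabulated |
|---|---|---|
| New AE, onset on drug | Yes | All tables |
| AE with onset on drug that worsens after the last dose | Yes, by its onset | All tables |
| New AE, onset within 30 days after the last dose | No | All-AE table; SAE table if serious |
| Condition present before the first dose that first worsens after the last dose | No | All-AE table; SAE table if serious |

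All four appear in the listings. The last two rows are missing from the TEAE incidence table, the treatment-emergent serious and nonserious tables, and the TEAE tables by intensity and relationship. They also carry no TEAE flag.

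**How much follow-up time lies outside the window (illustration)**

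Inputs: median exposure 8.3 months (inter-quartile range 4.2 to 14.6) in the earlier phase 3 trial, and the 12-month cap, both from Section 9.2.4; 30 days taken as 1 month, as in Table 1; 680 planned subjects, Section 9.2. Assumptions: that exposure applies here, treatment durations D are exponential, and no other dropout occurs.

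1. Stopping rate: λ = ln 2 / 8.3 = 0.0835 per month.
2. Mean time on drug up to Month 12: (1 − exp(−12λ)) / λ = (1 − 0.367) / 0.0835 = 7.58 months.
3. Share stopping before Month 12: 1 − 0.367 = 0.633, or about 430 of 680. Share stopping before Month 11, and so having a full 30 days: 1 − exp(−11λ) = 0.601.
4. Mean post-dose follow-up per subject, the expectation of min(1, 12 − D) over those with D < 12. Stops before Month 11 contribute 0.601. Stops between Months 11 and 12 contribute exp(−11λ) × [1 − (1 − exp(−λ)) / λ] = 0.399 × 0.0406 = 0.016. The sum is 0.617 month, or about 420 person-months over 680 subjects.
5. Share of follow-up after the first dose that lies outside the TEAE window: 0.617 / (7.58 + 0.617) = 7.5%.

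The exponential does not match the quoted quartiles exactly: it gives 3.44 and 16.59 months. Two other shapes anchored on the quoted median and quartiles barely change the answer:

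| Distribution | Stop before Month 12 | Post-dose months per subject | Share of time |
|---|---|---|---|
| Exponential | 63.3% | 0.617 | 7.5% |
| Weibull | 66.1% | 0.641 | 7.6% |
| Lognormal | 65.4% | 0.637 | 7.4% |

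**The case against.** The best case for the plan is that nothing is lost from the report. Post-dose events are in the all-AE table and the listings, and serious ones are also in the SAE table. Visit 1 is both inclusion and treatment initiation, on Day 1, so the planned pre-dose period is short and the all-AE table comes close to a table running from first dose to 30 days after the last. The AE that leads to stopping starts on drug and is counted. An on-treatment definition is also a legitimate choice, and a longer window lets in events that occur after progression or on the next systemic therapy.

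Most of this stands, and it limits the weight of the point. It does not remove it. The all-AE and SAE tables are not planned by intensity or relationship, they do not single out post-dose events, and the secondary objective is worded in terms of treatment-emergent events. If an on-treatment window is intended, the protocol does not say so or explain how it fits with the 30-day follow-up.

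Some stronger inferences are tempting but not supported:

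- That the undercount is greatest among subjects who stop for toxicity. This may be so, but nothing in the protocol documents it.
- That all worsening after the last dose is lost. Only pre-existing conditions that first worsen then are lost; an AE that began on drug remains a TEAE.
- That interruptions remove a large further block of time. The 70% in Section 7.1 is the proportion of subjects interrupted in the earlier trial, not time off drug. The protocol also treats interruption as a dose modification distinct from discontinuation. The wording needs clarifying, but it does not show an undercount.

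**Conclusion.** The point holds. As written, the rule leaves out of the treatment-emergent tables any new AE that starts after the last dose and any pre-existing condition that first worsens then, although these data are collected. One secondary objective is undercounted. The primary endpoint is defined by dose modifications due to AEs, not through TEAEs, and is not affected.

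The figure of about 7.5% is person-time. It rests on the earlier trial's exposure applying here and on an assumed distribution shape. It should not be read as the share of events lost: the documents give no post-dose AE rate, so that share is unknown. The gap concerns only subjects who stop before Month 12; those still on drug at Month 12 have no post-dose follow-up.

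Moderate: should be fixed. A reader might rate it as essential, but the study is descriptive, the events remain in other tables and the listings, and re-flagging recovers the counts.

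**What to change.** Redefine a TEAE in Section 9.7.2.4, and use the same definition in the SAP: an AE with onset, or worsening of a pre-existing condition, from the first dose of cabozantinib until 30 days after the last dose, or until the end of the 12-month follow-up if that is earlier. State that temporary interruptions lie within the window. In the TEAE tables, show events with onset after the last dose as a sub-row.

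If an on-treatment definition is what the sponsor wants, say so, give the reason, and tabulate post-dose AEs separately by intensity and relationship.

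The cost is one sentence and a change to the TEAE flag; no new data are needed. Counts will rise slightly and may take in some events after progression or after the start of a subsequent systemic therapy. The sub-row makes these visible.

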9.7.2.5 Endpoints and Evaluations

9.7.2.5.1 Primary Endpoint and Evaluations

The primary endpoint is the proportion of subjects with dose modifications due to AEs based on the investigator's decision (temporary interruption, dose reduction or discontinuation).

The primary analysis of the primary endpoint will be summarised descriptively for each line of treatment (second line or third and later line) and in total with their associated 2-sided 95% CIs based on the Clopper Pearson method using the Primary Safety population.

The impact of missing data on the analysis of the primary endpoint has been assessed. The precision of the proportion of subjects with dose modification due to AE has been calculated on different scenarios:

% of missing data	Number of evaluable subjects[a]	Precision[b]
5%	274	5.1%
10%	260	5.3%
15%	245	5.4%
20%	231	5.6%

- a From 289 subjects per line of treatment of the Primary Safety population
- b For a 95% CI and a proportion of subjects with dose modification of 75%

A proportion of missing data (ie, dose modification of cabozantinib due to AE) up to 20% is deemed acceptable in terms of precision of the estimation, meaning that, a proportion of more than 20% of missing data might impact the ability to assess the primary endpoint.

The proportion of missing data will be evaluated at time of the progress report and at time of the interim and final analyses.

A secondary analysis of the primary endpoint will be performed in a similar way and using the Safety population.

The proportion of subjects with dose modifications due to AEs related to cabozantinib (assessed by the investigator as certain, probable, possible or unlikely) will be described for the Safety population and for the Primary Safety population.

PAGE 34 OF 58

Additionally, this analysis will be repeated per AE relationship categories (certain/probable/possible/unlikely/not related/unassessable) (see definitions in Section 11.3.1).

The data for the primary endpoint will be listed using the Safety population.

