9.2.3 Study Population

The study population will consist of subjects diagnosed with advanced RCC, having received at least one prior VEGF-targeted therapy, who are starting cabozantinib tablets at the discretion of the treating physician and who consent to participate in the study.

In order to avoid bias related to physician-led subject selection, participating physicians will be asked to include all successive eligible subjects except those who refuse the collection of and/or access to their data until 340 subjects have been included in each subgroup (second and third and later line therapy).

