9.2.5 Study Place

Subjects will be recruited in countries where cabozantinib is marketed at the time of the study. It is anticipated that there will be approximately 100 study centres in 10 to 15 European countries. The number of sites in each country will be decided according to the size of the country.

Study centres will be proposed by the sponsor's local medical teams. Successive proposed sites that meet the feasibility criteria will be selected.

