9.5 Study Size

The sample size is based on the primary endpoint which is the proportion of subjects with dose modifications due to AEs based on the investigator's decision (temporary interruption, dose reduction or discontinuation) assessed for each line of treatment (second line therapy or third and later line therapy). In the open-label METEOR Study, any dose reduction due to an AE occurred in 59.8% of subjects and the study drug was interrupted in 70% of subjects. Overall, at least one dose modification (i.e. reduction or interruption) was reported for 76% of subjects treated with cabozantinib. The rate of treatment discontinuation due to an AE was 9.7% for subjects treated with cabozantinib.

Assuming a dose modification proportion of 75%, a sample size of 289 subjects is required to estimate a 2-sided 95% level of confidence of the dose modification proportion with a precision of $\pm 5\%$. To have a precision of at least 5% in second line therapy and third and later line therapy, a minimum of 289 subjects must be included in each line of treatment (second line and third and later line).

Assuming that up to 15% subjects will start the treatment with cabozantinib using scheduled regimens different from the recommended regimen at initiation (60 mg/day) [8, 9], the total included population will represent 680 subjects.

The recruitment of subjects in the concerned subgroup will be closed as soon as the 340 subjects are reached.

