9.9 Limitations of the Research Methods

This prospective, international, multicentre, noninterventional study will follow the real-life management of subjects in clinical practice.

The study will include subjects diagnosed with advanced RCC, having received at least one prior VEGF-targeted therapy, who are starting cabozantinib at the discretion of the treating physician. The decision to start treatment with cabozantinib will be taken prior to inclusion in the study. In order to avoid bias related to physician-led subject selection, participating physicians will be asked to include all successive eligible subjects except those who refuse the collection of and/or access to their data until 340 subjects have been included in each subgroup (second and third and later line therapy). Study centres will be proposed by the local medical teams. Successive proposed sites that meet the feasibility criteria will be selected.

The study will involve collection of primary data directly from health care professionals. The data collected are expected to provide real-world evidence of the use of cabozantinib in subjects with RCC. Only available evaluations as decided by the investigator based on local clinical practice will be collected. Where there are no data to report there will be no information recorded in the applicable section(s) of the eCRF. Therefore, the assessments performed and data provided from different study sites may vary depending on local clinical practice.

The outcome measures recorded will be as assessed by physicians in clinical practice. The effectiveness of treatment will be determined by investigators' assessment based on the methods available at their centres, rather than centrally by an independent radiology committee. Therefore, there may be inconsistency in the assessment of effectiveness between study sites and/or study physicians.

As this is a noninterventional study, no formal statistical testing will be performed and all the analyses will be primarily descriptive in nature.

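### The primary Clopper-Pearson intervals make no allowance for clustering by centre, which matters mainly for the total, and the total is a 1:1 quota average, not a real-life proportion.

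*Protocol*

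**What the plan says.** The endpoint is set in Protocol section 9.7.2.5.1: "The primary endpoint is the proportion of subjects with dose modifications due to AEs based on the investigator's decision". The same section reports it "for each line of treatment (second line or third and later line) and in total with their associated 2-sided 95% CIs", computed "based on the Clopper Pearson method using the Primary Safety population". The method is thus fixed in the protocol itself.

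The sample comes from many sites. Section 9.2.5 states: "It is anticipated that there will be approximately 100 study centres in 10 to 15 European countries". Section 9.2 has the drug given as the investigator directs, following the site's usual practice and the product's SmPC. Section 9.9 adds that "the assessments performed and data provided from different study sites may vary depending on local clinical practice".

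Recruitment runs by quota. Section 9.2.3 asks physicians to include successive eligible patients "until 340 subjects have been included in each subgroup (second and third and later line therapy"). Section 9.5 closes a subgroup once it reaches 340, and section 9.2 plans equal numbers in the two lines.

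On size, section 9.5 states: "Assuming a dose modification proportion of 75%, a sample size of 289 subjects is required", for a two-sided 95% interval of ±5 points in each line. Sections 9.5, 9.7.2.5.1 and 9.9 mention no centre effect, ICC, design effect or weighting of the total.

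**The concern.** Clopper-Pearson treats the subjects as one sample of independent binary outcomes. Here the outcome is a physician's choice to interrupt, reduce or stop the drug, and several subjects share a centre. If centres differ in how readily they modify the dose, the effective sample size is smaller than the head count, and the interval claims more precision than the data carry. The study has no formal test, and ±5 points is its only sample-size criterion, so the interval is the main inferential product.

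The second issue is separate and concerns only the total. Section 8.1 asks about use in real-life settings, but the pooled proportion weights the lines by quota and not by how often each occurs in practice. Section 7.2 says that tolerability in second versus later lines is unknown, so equal rates cannot be taken for granted.

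**Working it through.** **Reproducing the plan's figures.** n = 1.96² × 0.75 × 0.25 / 0.05² = 288.1, rounded up to 289. With 15% not starting on the recommended regimen, 289/0.85 = 340 per line and 680 in total. The missing-data table in section 9.7.2.5.1 also reproduces: n = 274, 260, 245 and 231 give half-widths of 5.1, 5.3, 5.4 and 5.6 points. All of these figures use a design effect of 1.

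**Inputs for clustering.** From the protocol: 289 per line, 578 in total (2 × 289), about 100 centres and p = 75%. The mean number per centre is therefore m = 2.89 per line and 5.78 in total. Assumed, because the protocol gives neither: ICC 0.02, 0.05 or 0.10, and centre-size CV of 0 or 1.

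**Formula.** DE = 1 + ((1 + CV²)m − 1) × ICC. The half-width grows by √DE. The Wald half-widths under independence are 4.99 points per line and 3.53 in total. For example, in total with CV 1 and ICC 0.10: DE = 1 + (2 × 5.78 − 1) × 0.10 = 2.056, and √2.056 = 1.43. Coverage is that of the planned Clopper-Pearson interval in a beta-binomial simulation of 20,000 runs per setting. In the simulation, CV 0 means equal expected centre sizes, so realised sizes are only near-equal.

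| | ICC | DE, CV 0 | DE, CV 1 | Widening, CV 0 / CV 1 | Half-width (points), CV 0 / CV 1 | Coverage, CV 0 / CV 1 |
|---|---|---|---|---|---|---|
| Per line | 0.02 | 1.04 | 1.10 | 2% / 5% | 5.1 / 5.2 | 95.3% / 94.7% |
| Per line | 0.05 | 1.09 | 1.24 | 5% / 11% | 5.2 / 5.6 | 94.3% / 92.7% |
| Per line | 0.10 | 1.19 | 1.48 | 9% / 22% | 5.4 / 6.1 | 92.4% / 89.4% |
| Total | 0.02 | 1.10 | 1.21 | 5% / 10% | 3.7 / 3.9 | 94.5% / 93.2% |
| Total | 0.05 | 1.24 | 1.53 | 11% / 24% | 3.9 / 4.4 | 92.8% / 89.3% |
| Total | 0.10 | 1.48 | 2.06 | 22% / 43% | 4.3 / 5.1 | 89.2% / 82.8% |

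With ICC = 0, coverage is about 96%, because Clopper-Pearson is conservative. The total suffers more because subjects per centre double.

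A yardstick from the plan: section 9.7.2.5.1 accepts up to 20% missing data, which means 5.6 points per line. At ICC 0.05 and CV 1, clustering alone brings the per-line half-width to 5.6 with nothing missing.

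**Quota weighting.** Let s be the real second-line share. The quota total is (p2L + p3L)/2 and the real-mix total is s·p2L + (1 − s)·p3L. The difference, quota minus real, is (s − 0.5) × (p3L − p2L). At assumed rates of 70% and 80% and s = 0.7, it is 0.2 × 10 = 2 points (75% reported, 73% real). At s = 0.3 it is −2 points. The Clopper-Pearson half-width of the total is 3.6 points (434 of 578). At assumed rates of 65% and 85%, s = 0.7 gives 4 points. If the lines have equal rates, the shift is zero.

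**Do the quotas narrow the interval?** At 70% and 80%, the stratified half-width is 1.96 × √((0.21 + 0.16)/(4 × 289)) = 3.51 points, against 3.53 for the pooled binomial. They do not.

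**The case against.** The case for leaving the plan alone has several sound parts.

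- **No ICC is documented.** The protocol gives neither an ICC nor a centre-size distribution, so it cannot be shown that these intervals are too narrow. This stands, and the claim is conditional.
- **Clopper-Pearson has slack.** At 217 of 289 its half-width is 5.14 points, against a design-effect-adjusted Wald half-width of 5.09 to 5.23 at ICC 0.02. This stands: per line, the effect at low ICC is absorbed.
- **Section 9.9 speaks of assessments and data.** A reader might infer that the protocol concedes site variation in dosing decisions. It does not. That section leads to a caveat on effectiveness, and section 9.8.3 requires dates and reasons for AE-related dose changes in the source documents. The reason to expect clustering is that the endpoint is an investigator's decision under site practice.
- **The total is not the main target.** The sample size and the missing-data table are per line, the 1:1 plan is stated openly, and the protocol nowhere says that the total reflects the real-life mix. This stands and limits the quota point to one estimate. That total still appears unlabelled in a study of real-life use.
- **The analyses are descriptive, and detail can go to the SAP.** Section 9.7.2.1 rules out formal testing, so no decision turns on these intervals. But the protocol names the interval method itself, so this is more than detail left open. The country breakdown in section 9.7.3 shows some heterogeneity but does not correct the interval.

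A reader might also infer that filling the sample by quota makes the interval too narrow. The stratified calculation shows otherwise: the quotas change what the total estimates, and only clustering can make it falsely precise.

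**Conclusion.** The point holds in a limited form. The protocol fixes independence-based intervals, and a sample size with a design effect of 1, for an endpoint where correlation within centre is plausible. If it is present, the intervals are likely too narrow, mainly for the total: 5 to 43% over the assumed ICC and CV ranges, with coverage about 94.5% down to 83%. Per line the range is 2 to 22%, with coverage about 95% down to 89%. A material per-line shortfall needs a high ICC or strongly unequal centres.

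Separately, the total is a quota average of the lines. It is close to 1:1 provided both quotas fill and similar shares start at the recommended dose. Its distance from a real-mix figure depends wholly on assumed rates and mix: zero if the lines agree, 2 points in the 70/80%, 70:30 example. The documents do not support calling the per-line estimates biased or the total wrong for a purpose that the protocol does not claim.

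**What to change.** 1. Keep the per-line estimates as primary. Beside each planned interval, per line and in total, report a 95% interval with centre as the cluster: Clopper-Pearson on n divided by the estimated design effect (not letting it fall below 1), or a GEE logit with centre-robust standard errors. State the estimated ICC.
2. Label the total a 1:1 quota-weighted average and show the actual number per line.
3. Add a supplementary total weighted to the line mix among consecutive inclusions while both subgroups were open, with a variance that reflects the weights.

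The cost is a short text change and a little more analysis. Centre and line are already recorded (section 9.7.2.3 tabulates by both). The intervals become somewhat wider. Before any clustering, weighting to 70:30 at rates of 70% and 80% takes the total's half-width from about 3.5 to about 3.9 points. The observed mix describes only the participating sites, which the sponsor's local teams propose (section 9.2.5), so the supplementary total should carry that caveat.
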